5.2 Randomization

Subjects will be randomly assigned in a 1:1 ratio to Gan & Lee Insulin Glargine Injection or Lantus® treatment. Subject randomization will use a randomly permuted block design with varying block sizes and without stratification.

Registration and randomization will take place using a centralized Interactive Web Response System (IXRS). At registration, the IXRS will assign a unique subject identification number that will be used on all of that subject's eCRFs and serious adverse event (SAE) report forms.

This is an open-label study, however, to avoid the introduction of operational bias into final study results and to increase the interpretability and reliability of the data, certain roles of the Sponsor and study team will be blinded. Details are provided in the Data Blinding and Documentation of Aggregate Data Dissemination Plan (hereafter referred to as the Blinding Plan).

6. Endpoints and Covariates

6.1 Primary Endpoint

6.1.1 Immunogenicity

- The percentage of subjects in each treatment group who develop treatment-induced AIAs, defined as either newly confirmed positive AIA development or important increase (at least a 4-fold) in AIA titers after baseline and up to visit Week 26 (refer to Section 7.2 for detailed definition).

6.2 Key Secondary Endpoint

6.2.1 Efficacy

- The change in HbA1c from baseline at visit Week 26

6.3 Other Secondary Endpoints

6.3.1 Immunogenicity

- The percentage of subjects in each treatment group with negative AIA at baseline who develop confirmed positive AIA after baseline and up to visit Week 26
- The percentage of subjects in each treatment group with confirmed positive AIA at baseline and at least a 4-fold increase in titers after baseline and up to visit Week 26
- The mean change from baseline in each treatment group in AIA titers after baseline and up to visit Week 26. Though not specified in the protocol, this analysis is planned for the subset of subjects with confirmed positive AIA at baseline
- The percentage of subjects in each treatment group with confirmed positive AIA after baseline and up to visit Week 26 who develop any anti-insulin neutralizing antibodies after baseline and up to visit Week 26
- The percentage of subjects in each treatment group with confirmed positive AIA after baseline and up to visit Week 26. This summary is planned to include all subjects regardless of subject's status of AIA at baseline

6.3.2 Safety

- The incidence and severity of all treatment-emergent adverse events (TEAE) and the following subgroups:
 - Hypoglycemia, which will be fully documented in the Hypoglycemic Events Record, using data from subject report (symptomatic), FBG from central lab, study issued glucometer and CGM
 - SAEs, including fatal events
 - Adverse events leading to termination of the study treatment and/or early withdrawal from the study
 - IP-related AEs
 - Injection site reactions
- The incidence of clinically significant laboratory abnormalities
- The incidence of clinically significant abnormalities in electrocardiogram (ECG) and vital signs

6.3.3 Efficacy

- The number and percentage of subjects who achieve a FBG test result of ≤ 8.0 mmol/L (≤ 144.0 mg/dL) at visit Week 26
- The number and percentage of subjects who achieve a HbA1c of $< 7.0\%$ at visit Week 26

6.4 Exploratory Endpoints

- Retrospective CGM hypoglycemic rate
- Time in hypoglycemia and hyperglycemia event based on CGM data

7. Definitions

7.1 General

1) Actual Treatment

The actual treatment received is defined as the IP treatment the subject received during the study, regardless of the treatment the subject was allocated to by randomization. If a subject receives both Gan & Lee Insulin Glargine Injection and Lantus® during the study period for whatever reason, then the actual treatment will be based on the treatment taken on the majority of days during the study.

2) Assessment after EOT

Assessment after EOT is defined as AIA/HbA1c assessment documented after date of EOT visit. If date of EOT visit is missing it is defined as assessment documented after date of last dose of IP + 1 day (to consider assessments of subjects who perform the visit assessment before daily dose of IP).

3) Average Daily Dose of IP

Average Daily Dose is defined as captured on the Average Daily Dose of Study Drug CRF page.

4) Baseline

For each endpoint of interest, unless otherwise noted, the study baseline is defined as the last non-missing assessment taken prior to or on the date of the first dose of study IP. For subjects whose treatment assignment is randomly assigned but not dosed after the randomization visit, the baseline is defined as the last non-missing assessment prior to or on the date of randomization.

5) Change from Baseline

Change from baseline is defined as (value at post-baseline visit – value at baseline).

6) Completer Week 26

A subject is defined as a Completer Week 26 if the answer to the question "Did the subject complete the study?" is "Yes" on the End of Study CRF page and who received IP for at least 22 weeks.

7) Dates of First and Last Dose

The date of first dose of IP is defined as the date of first dose of IP documented on the First Dose of Study IP CRF page and the date of last dose of IP is defined as the date of last dose of IP documented on the End of Study 2 CRF page. If no date of first dose of IP is available, the date of randomization will be selected as the date of first dose of IP. If no date of last dose of IP is available, the date of completion/discontinuation documented on the End of Study CRF page will be selected as the date of last dose. If date of last dose of IP is not available and subject is lost to follow up based on End of Study CRF page, date of last scheduled visit or date of last telephone contact where an average daily dose is recorded, will be used as the date of last dose of IP.

8) Diabetes Disease Duration

The duration of diabetes is defined as the number of years from the date of original diagnosis of Type 2 Diabetes Mellitus to the date of randomization (presented in full years):

$$(\text{date of randomization} - \text{date of Type 2 diagnosis} + 1) / 365.25$$

If the date of Type 2 Diabetes Mellitus is partially missing, then the following imputation rules will be applied:

- Missing day, but month and year are present: the day will be imputed as the 1st of the month.

Sponsor: Gan & Lee Pharmaceuticals, USA Corporation
 Protocol no: GL-GLAT2-3002

Statistical Analysis Plan
 Version Date: 16-Nov-2020

- Missing day and month but year is present: the day and month will be imputed as July 1 or date of consent, whichever is earlier.
- Date completely missing: no imputation will be done, and diabetes disease duration will also be missing.

9) Dosing Regimen

- Daily (QD): Dosing where the answer to the question "Was the subject compliant with QD dosing since the previous visit?" is Yes on all Average Daily Dose of Study Drug CRF pages.
- Twice daily (BID): Dosing at least once where the answer to the question on the Average Daily Dose of Study Drug CRF page "Was the subject compliant with QD dosing since the previous visit?" is No and "Subject dosed BID on one or more days" is ticked at least once.

10) Double Average Daily Dose

Double Average Daily Dose is defined as having at least double the average daily dose compared to the first average daily dose after randomization at any subsequent average daily dose assessment.

11) Eligibility-Related Important Protocol Deviation (ERIPD)

Eligibility-related important protocol deviations are important protocol deviations coded to the Inclusion Criteria or Exclusion Criteria categories (refer to Appendix 4 for details).

12) End of Treatment visit

The End of Treatment visit (EOT) is defined as the visit Week 26. Any subject who discontinues from treatment before visit Week 26 will have the Visit 9 procedures performed for their EOT visit.

13) Exposure

- Duration of therapy (presented in weeks with one decimal place)

Duration of therapy is defined as (date of last dose – date of first dose + 1)/7.

- Estimated total cumulative dose (presented in U with one decimal place)

The estimated total cumulative dose for a given subject will be calculated using the following formula:

$$\sum_{i=2}^{n_c} (\text{Number of Days between } C_i \text{ and } C_{i-1}) * \text{Average Daily Dose}_i$$

where C_i represents the subject's i^{th} contact (including clinic visits as well as telephone contacts) and n_c represents the number of contacts for the given subject. Missing data will not be imputed.

14) Imputation of start and stop dates of AEs (for determination if TEAE only) and prior and concomitant medication (for determination of prior and concomitant only):

Sponsor: Gan & Lee Pharmaceuticals, USA Corporation
Protocol no: GL-GLAT2-3002

Statistical Analysis Plan
Version Date: 16-Nov-2020

- **Start Date:** If only 'day' is missing, and the month and year are not the same as the date of first dose of IP, then impute day with '01'. Otherwise, if the month and year are the same as the date of first dose of IP, use the date of first dose of IP. If 'day' and 'month' are missing, and 'year' is not missing, then impute month and day with month and day of the date of first dose of IP (assuming same 'year'). Otherwise, if year is not the same year, then impute day and month with January 1st. If the start date is completely missing, it will be set to the date of first dose of IP. For prior and concomitant medication if the start date is completely missing and "Was the medication/therapy taken prior to the study (informed consent signature)?" is answered "Yes", no imputation will be done.
- **Stop Date:** If only 'day' is missing, impute day with last day of the month. If 'day' and 'month' are missing, and 'year' is not missing, then impute month with '12' and day with '31' (or date of study discontinuation/completion if the year is the same as the year of discontinuation). If the stop date is completely missing, it will be set to the date of study discontinuation/completion. A stop date will not be applied to ongoing AEs and prior and concomitant medications.

15) Menopausal Status

Menopausal status is defined as either pre-menopausal if the answer to "If female, is the subject of childbearing potential?" is Yes and post-menopausal if the answer is No on Demographics CRF page.

16) Obese

Obese is defined as having a body mass index (BMI) of 30.0 or greater and non-obese is any BMI less than 30.0.

17) Other Anti-diabetes Medications (OAM)

An OAM is defined as any medication from the Prior/Concomitant Medications CRF page where the answer to the question "Was this medication an Other Anti-diabetic Medication?" is Yes and the route is Oral.

18) Overall Subject Average Daily Dose

Overall Subject Average Daily Dose (OSADD) is defined as the average of all non-missing average daily doses recorded throughout the study after randomization (including scheduled and unscheduled assessments). The study diagram shows that the number of Average Daily Dose assessments is scheduled to be collected at seven in-person visits and 5 telephone visits for each subject (See Section 8 of the Protocol).

19) Overdose

Overdose is identified based on investigator discretion, as recorded in the Overdose CRF page. Overdoses are further classified as being related to an adverse event and as being related to a hypoglycemic event in the Overdose CRF page.

Overdose is also identified programmatically as double average daily dose (see above definition), based on information collected in the Exposure CRF page.

Additionally, hypoglycemic events associated with overdose are captured in the Hypoglycemia CRF page.

20) Previous Exposure to Lantus®

Previous Exposure to Lantus® is defined as No Previous Exposure if no Lantus® treatment is documented within 6 months prior to first dose of IP on the prior/concomitant medications CRF page and as Previous Exposure if at least one dose of Lantus® is documented within 6 months prior to first dose of IP (between and including study day -182 and study day -1).

21) Prior and Concomitant Medications

Prior medications are defined as those with a start date prior to the date of randomization and an end date on or before the date of randomization.

Concomitant medications are defined as those ongoing at the date of randomization or with a start date on or after the date of randomization.

22) Study Day

Study Day 1 is defined as the date of first dose of IP. For subjects whose treatment assignment is randomly assigned but not dosed, Study Day 1 is defined as the date of randomization assignment. For dates prior to Study Day 1, the Study Day is calculated as:

$$\text{Study Day} = (\text{Date of Interest/Assessment} - \text{Date of Study Day 1})$$

For dates post Study Day 1,

$$\text{Study Day} = (\text{Date of Interest/Assessment} - \text{Date of Study Day 1} + 1)$$

23) Study Completers

Subjects with non-missing baseline and scheduled visit Week 26 assessment of AIA and who received IP for at least 22 weeks will be used for the analysis.

24) Thyroid Function Abnormality

Thyroid Function Abnormality is defined as any post-baseline thyroid-stimulating hormone (TSH) or free thyroxine (T4) from the central laboratory that is outside the normal range.

25) Time from First Dose of IP to Early Treatment Discontinuation

The time from first dose of IP to early treatment discontinuation will be defined as:

$$(\text{date of last dose of IP} - \text{date of first dose of IP} + 1)$$

Subjects who completed the study will be censored at the date of last dose of IP or study day 182 (Week 26).

26) Treated with IP

All randomized subjects satisfying any of the following criteria will be considered as having received any IP:

- for whom a date of first dose of IP is documented on the First Dose of Study IP CRF page or
- for whom a date of last dose of IP is documented on the End of Study CRF page or
- for whom an average daily dose is documented on the Average Daily Dose of Study Drug CRF page

will be considered as having received any IP. Subjects not satisfying any of the above criteria will be considered as having not received any IP.

Sponsor: Gan & Lee Pharmaceuticals, USA Corporation
Protocol no: GL-GLAT2-3002

Statistical Analysis Plan
Version Date: 16-Nov-2020

27) Visit Window Week 12/26

Visit windows for visit Week 12 and 26 are defined as:

- visit Week 12 \pm 1 week (Study Day 84 \pm 7)
- visit Week 26 \pm 4 weeks (Study Day 182 \pm 28).

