## **11. SAFETY MEASUREMENTS AND VARIABLES**

### **11.1 Adverse Events**

The definitions and reporting procedures provided in this protocol comply with the current CFR 21 Part 312. An adverse event is any untoward medical occurrence or worsening of a pre-existing condition, regardless of the relationship to the investigational medicinal product. An adverse event can therefore be any unfavorable or unintended sign, including an abnormal laboratory finding, symptom or disease temporally associated with the use of an investigational medicinal product whether or not considered related to the investigational medicinal product.

Adverse events will be recorded beginning at the screening visit. Nonserious adverse events will be recorded from the time informed consent is signed through the subject's last study visit (or termination if the subject terminates early from the study for any reason). Serious adverse events will be collected from the time informed consent is signed through and including 30 calendar days after the last dose of treatment with IP.

The Investigator or designee will record all adverse events on the eCRF, regardless of the Investigator's assessment of causality, including a description of the event, severity, time of occurrence, duration, any action (e.g., treatment and follow-up tests), the event outcome, and the Investigator's assessment of the relationship to the study treatment.

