7.3 Safety

1) American Diabetes Association (ADA) Severe Hypoglycemic AE

A hypoglycemic AE will be classified as "ADA severe" if the answer to the question "Was third party intervention required for this episode of hypoglycemia?" is Yes on the Hypoglycemia CRF page as mentioned in the ADA hypoglycemia position statement (3).

ADA Severe Hypoglycemic AE should not be confused with hypoglycemia AEs that are graded severe (Grade 3) per National Cancer Institute Common Terminology Criteria for Adverse Events (NCI CTCAE) grade (see Section 11.8.1.1).

2) Adverse Event Leading to Discontinuation of IP

An AE will be classified as an AE leading to discontinuation of IP if the answer to the question "Did the adverse event cause the subject to be discontinued from the study?" is Yes on the AE CRF page.

3) Hypoglycemic AE

An AE will be classified as a hypoglycemic AE if the answer to the question "Is this a hypoglycemic event?" is Yes on the AE CRF page.

4) Injection Site Reactions

Injection site reactions will be identified using the High Level Term = "Injection site reactions".

5) IP-related adverse events

An AE will be classified as related to IP if the relationship to study treatment is Possibly Related, Probably Related, or Definitely Related. Additionally, if the relationship is missing, then the AE will be deemed related to IP.

6) Measured Hypoglycemic AE

A hypoglycemic AE will be classified as measured if the lowest blood glucose value documented on the Hypoglycemia page is less than or equal to 3.0 mmol/L.

7) Persistent/Non-persistent Hypoglycemic AE

Hypoglycemic event with Time in hypoglycemia (see definition in Section 7.4) greater or equal to an hour (per CGM) would be classified as persistent. A hypoglycemic event with Time in hypoglycemia below an hour (per CGM) would be classified as non-persistent.

8) Symptomatic Hypoglycemic AE

A Hypoglycemic AE will be classified as symptomatic if the answer to the question "Was subject aware of symptoms?" is Yes on the Hypoglycemia CRF page.

9) Treatment-emergent adverse events (TEAE)

A TEAE is defined as an AE occurring on or after the date of the subject's first dose of IP and on or before the day of last dose for AEs but not more than 30 days after the subject's last dose of IP for SAEs.

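### SAP 7.1 definition 14 imputes partial start dates to the first IP dose without checking a recorded stop date, so some AEs that ended before treatment count as TEAEs and some stopped drugs count as concomitant

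*SAP*

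**What the plan says.** SAP 7.1 definition 14 imputes dates solely to decide TEAE status and prior/concomitant status. It sends a start date to the first IP dose in three cases:

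- Day missing, month and year known: "if the month and year are the same as the date of first dose of IP, use the date of first dose of IP". A different month becomes the 1st of that month.
- Only the year known: if it is the first-dose year, the first-dose day and month are used. Any other year becomes 1 January.
- No date at all: "If the start date is completely missing, it will be set to the date of first dose of IP". There is one exception. It opens "For prior and concomitant medication if the start date is completely missing and" and also requires a Yes to the CRF question whether the drug was taken before consent. No imputation is then made.

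The stop-date rule only fills gaps, for example "If only 'day' is missing, impute day with last day of the month". It does not compare stop with start.

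The imputed start then feeds two definitions. In SAP 7.3 definition 9, "A TEAE is defined as an AE occurring on or after the date of" the first IP dose. In SAP 7.1 definition 21, prior medications are "those with a start date prior to the date of randomization and an end date on or before the date of randomization", whereas a start on or after randomization is enough by itself to make a drug concomitant.

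Protocol 11.1 states "Adverse events will be recorded beginning at the screening visit", and Protocol 9.1 places that visit between Day -14 and Day -1. Pre-treatment AEs are therefore in the database by design.

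**The concern.** Moving an unknown start to first dose is sensible when the record cannot show whether the event came before or after treatment. Here the rule also applies when the record does show it. An AE with a recorded stop before first dose cannot have begun on treatment, and a drug stopped by randomization was not started after it. In both cases the rule overrides a recorded fact and can create a start later than the stop.

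At stake are the TEAE tables in SAP 11.8.1, including the hypoglycemic TEAE counts, and the prior and concomitant medication tables in SAP 11.5.1, including the separate insulin summaries. A misclassified AE leaves the listing of non-treatment-emergent events and enters the incidence tables.

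**Working it through.** The plan states no figure to reproduce. The check applies the written rules to example records and then asks how far the rule reaches.

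**Inputs.** Imputation: SAP 7.1 definition 14. Classification: SAP 7.1 definition 21 and SAP 7.3 definition 9. IP is issued at the randomization visit (Protocol 9.2), so a start imputed to first dose falls on or after randomization. Dates assumed for illustration: consent 06-Sep-2018; randomization and first dose 20-Sep-2018. All drugs below carry the CRF answer that they were taken before the study.

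| Record | Recorded start | Recorded stop | Start under definition 14 | Status as written | Status with the fix |
|---|---|---|---|---|---|
| AE 1 | Sep-2018 | 12-Sep-2018 | 20-Sep-2018 | TEAE | not TEAE |
| AE 2 | 2018 | 12-Sep-2018 | 20-Sep-2018 | TEAE | not TEAE |
| AE 3 | none | 12-Sep-2018 | 20-Sep-2018 | TEAE | not TEAE |
| Drug A | Sep-2018 | 15-Sep-2018 | 20-Sep-2018 | concomitant | prior |
| Drug B | 2018 | 30-Jun-2018 | 20-Sep-2018 | concomitant | prior |
| Basal insulin | 2018 | 20-Sep-2018 | 20-Sep-2018 | concomitant | prior |
| Drug C (control) | 2017 | 30-Jun-2018 | 01-Jan-2017 | prior | prior |

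The three AEs and Drugs A and B all receive a start after their own stop. Drug C shows that an earlier-year start is classified correctly. A drug with no start date and the same CRF answer is not imputed at all.

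**How many screening days the rule reaches.** For a first dose spread evenly over a month of L days, the chance that a day k days earlier lies in the same month is (L - k)/L. Averaged over k = 1 to 14 (mean k = 7.5), this is 1 - 7.5/L:

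- L = 28: 1 - 0.268 = 0.732
- L = 30: 1 - 0.250 = 0.750
- L = 31: 1 - 0.242 = 0.758

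Over a whole year there are 365 × 14 = 5,110 pairs of first-dose day and screening day. Each month boundary separates 14 + 13 + ... + 1 = 105 pairs. The same-month share is 1 - (12 × 105)/5,110 = 0.753, and the same-year share is 1 - 105/5,110 = 0.979.

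These are shares of screening days. They say how often a day-missing or year-only AE onset in screening would be moved, if onsets are even over 14 days. The record is then misclassified only if its stop date also precedes first dose. The documents give neither the frequency of partial dates nor that second share.

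**Basal insulin.** Inclusion criterion 4b (Protocol 8.4.1) requires at least 6 months of insulin, with no change of type or brand in the 6 months before screening. A true start in the first-dose month is therefore excluded for an eligible subject. A start in the same year as screening needs screening in about July or later (1 January plus 6 months).

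**The case against.** The strongest defence is that imputing to first dose is cautious: it over-counts TEAEs rather than missing them, and it treats both arms alike. The TEAE definition speaks of events occurring from first dose onward, so one can read it as excluding an event already recorded as resolved. Partial dates should also be uncommon. AEs are recorded with time of occurrence and duration (Protocol 11.1), hypoglycemic events have their own prospective record (Protocol 8.6.1), medication entries call for dates (Protocol 8.5.9), and SAP 10.2 provides programming checks and two dry runs before lock.

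Much of this stands as a limit on size. It does not supply the missing rule. Caution is a reason to impute when timing is unknown, not when a recorded stop settles it. Definition 14 exists to decide TEAE status, so code that follows it uses the imputed start. The favourable reading of the TEAE definition is possible, but the SAP does not state it. The data checks can reduce partial dates but do not say how to classify those that remain.

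A reader might infer more than the documents support:

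- That about three quarters of screening AEs become false TEAEs. The 75% describes day-missing onsets that would be moved; it is not an error rate.
- That the insulin tables are broadly distorted because long-standing drugs often have only a year recorded. Earlier-year starts go to 1 January and classify correctly, which leaves only the narrow basal-insulin case above.
- That the CRF answer on use before the study needs its own cap at consent. Once the stop date decides status, a drug stopped by randomization is prior, and one still ongoing at randomization is concomitant whatever its start. The cap would change no classification, and the SAP has no such cap for fully missing dates to extend: it leaves them unimputed.

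**Conclusion.** The point holds as a defect in a stated rule. Followed literally, definition 14 produces starts after stops, false TEAEs and false concomitant medications. It is confined to records that have both an incomplete start caught by the rule (same month as first dose, same year if only the year is known, or fully missing outside the medication exception) and a stop date before first dose (AEs) or on or before randomization (drugs). Complete dates and starts in an earlier month or year are not affected.

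The number of such records cannot be derived and is probably small. The 75% and 98% reach figures rest on onsets spread evenly over a 14-day screening period and first doses spread evenly over the year. The primary AIA and key secondary HbA1c analyses do not use these dates, so no primary conclusion is at risk. The correction should be made because it is cheap and the present rule contradicts recorded data.

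**What to change.** Add two sentences to SAP 7.1 definition 14:

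1. If the recorded stop date of an AE, or a partial stop date taken at its latest possible value, is before the first IP dose, the AE is not treatment-emergent, and the imputed start may not be later than the stop date.
2. A medication with a partial or missing start date whose stop date, on the same basis, is on or before randomization is classified as prior.

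The existing stop-date rule already fills a missing day with the last day of the month, so the latest-value basis needs no new convention there. No consent-date cap is needed.

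The cost is the added text and a small change to the date-derivation code, using data already collected. SAP section 3 foresees a final version before database lock, which is the natural place for it.
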